4.3 Other Variables and Covariates

We will capture the following additional demographic, clinical, and disease variables:

- Demographic data: Age, Marital Status, Race, Ethnicity, Employment Status, Clinician, Primary Language, Country of Birth, Education Level.
- Previous medical history: Comorbidities, Smoking History, and Family History of Malignancies.
- Disease characteristics: Date of Diagnosis, Site of Disease, Site(s) of Metastasis, if applicable, Histology/Grade/Pathologic Parameters, PSA, Stage, Somatic Molecular Profile, Date of Collection of Tissue Analyzed, Type of Tissue Analyzed.
- Treatment data: Date of Surgery, Date of Radiation, Dose of Radiation, Systemic Therapy.
- Treatment outcomes data: Toxicity, Dose Reduction, Reason for Dose Reduction, Response, Progression, Survival.

4.4 Statistical Analysis Plan

4.5 Statistical Methods – General Aspects

4.5.1 Primary Objective(s): Calculation of Epidemiological Measure(s) of Interest (e.g. descriptive statistics, hazard ratios, incidence rates, test/retest reliability)

Primary Endpoints

With regards to the primary endpoint, at the completion of the study, the proportion of patients who complete germline testing among all who are enrolled to the study will be computed. A sample size of 50 patients produces a two-sided 95% confidence interval on the proportion with a width ranging from 0.27 to 0.29 when the observed proportion ranging from 0.3 to 0.7. For proportions, 95% confidence intervals will be calculated using the exact method.

We will also compute the proportion of patients who completed germline testing for all eligible prostate cancer patients evaluated in clinic but not enrolled into this study during the study period. Characteristics between these two groups will be compared using Fisher's Exacts or Wilcoxon Rank Sum tests. The proportion of patients who underwent germline testing in the intervention vs non-intervention cohorts will be compared using Fisher's exact test.

4.5.2 Secondary Objective(s): Calculation of Epidemiological Measure(s) of Interest (e.g. hazard ratios, incidence rates, test/retest reliability)

Secondary endpoints including germline mutation frequency, patient understanding of germline testing, and medical management from germline testing will be described using descriptive statistics such as bar graphs, box plots, percentages, means and standard deviations, etc.

4.5.3 Exploratory Objective(s): Calculation of Epidemiological Measure(s) of Interest (e.g. hazard ratios, incidence rates, test/retest reliability)

- Associations between clinical factors and pathogenic germline alterations will be evaluated using Odds Ratio.
- Impact of germline testing on prostate cancer and cancer surveillance management will be qualitatively described.

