The patient will then have an opportunity to ask questions. If a patient wishes to proceed with testing, they will sign the standard consent to proceed with germline testing and the patient's clinician will be notified of intent to proceed with germline testing. Patients can elect to decline testing, defer testing to a later time, or request referral to genetic counseling to discuss the testing. We will track patterns of patient decision making following the educational intervention. Upon a patient deciding to pursue testing, testing will consist of a prostate cancer germline panel with a commercially available blood or saliva-based assay. Following the educational intervention, the patient will be asked to complete a short patient education and satisfaction questionnaire (Appendix D). Upon receipt of the results, the coordinator will alert the patient's clinician, who will then share the results with the patient either in clinic or by phone. If the results show a

pathogenic germline mutation, the patient will be referred to see the UCSD cancer medical genetics clinic for consultation with a genetics counselor. Additionally, the patient can elect to see a genetics counselor independent of the test results once the test results are reviewed. If a patient pursues genetic testing, following receipt of results, the patient's clinicians will be asked to complete a short survey on to assess how the results of germline testing affected the patient's current and future management (appendix D). There will be capacity for patients to complete questionnaires electronically. Additionally, to systematically understand the scope of questions asked by patients which will provide opportunity to optimize the educational intervention, we will record the educational sessions.

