3.5 Participant Follow-up

Patients will be followed for 24 months following the educational session. We will capture deferred decisions to pursue germline testing during the 24-month follow up period. Data on oncologic outcomes, prostate cancer management, and cancer surveillance will be obtained from the medical record.

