Appendix B: Family History Questionnaire

Patient Name:

Medical Record #

Family History Questionnaire

Part 1: Personal history information

Have you had any genetic testing of your **tumor** tissue? Yes No Not sure
(examples: Foundation, Guardant, Tempus, or Caris testing)

Health history/ancestry:

Ancestry (e.g. Swedish, Japanese, English)

Mother's side:

Father's side:

Any Ashkenazi Jewish Ancestry? Yes No What side of the family?

Ever had a colonoscopy? Yes No If yes, any history of colon polyps?

Other health issues you'd like to share

Have you had genetic counseling because of your family history of cancer before? Yes No
Not sure

If so, where was the genetics consultation done? UCSD Elsewhere:

Genetic Testing History

Have you ever had genetic testing for cancer risk before?

Yes No Not Sure

Observational Study Protocol Form

Version 3.0

Form Doc ID: AZDoc0059948

Parent Doc ID: SOP LDMS_001_00164328

If yes, please describe (what test, what year completed if known)

What were the results?

gene

A mutation was found in the

(Important: Please bring copies of results)

gene

No mutations were found

My results were "uncertain" in the

I'm not sure

Please describe any other genetic testing findings or issues:

Yes No Not Sure

If yes, please describe which relative(s) and their results, if known (**Important: If possible, please bring copies of reports**)

Part 2. Your children:

How many children (living and deceased)? _____

Please list your sons and daughters on the rows below (if you need more rows, please use the back of this form):

Relative	Ever diagnosed with cancer?	Check if deceased	Current age/ Age at death	Cancer Type	Age at diagnosis
Son  Daughter 	Y  N 				
Son  Daughter 	Y  N 				
Son  Daughter 	Y  N 				

Son 	Daughter 	Y 	N 				
Son 	Daughter 	Y 	N 				

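### The plan sets no common source or time window for counting germline tests in the two cohorts, so fuller and longer capture in enrolled men could inflate the primary comparison

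*Combined protocol and SAP*

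**What the plan says.** The first primary endpoint (section 4.2) compares the proportion tested among enrolled men with the proportion tested among eligible men who did not enrol. Section 4.5.1 gives the analysis: "The proportion of patients who underwent germline testing in the intervention vs non-intervention cohorts will be compared using" Fisher's exact test.

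**Enrolled men.** Section 3.1 states "We will track patterns of patient decision making following the educational intervention". A man who wants testing signs the testing consent after the session, and the coordinator handles the incoming result and alerts the clinician. Section 3.5 follows men for 24 months after the session and adds "We will capture deferred decisions to pursue germline testing during the 24-month follow up period".

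**Comparators.** Sections 3.2 and 4.1.2 define them as eligible men who declined or were not approached, with education left to the treating team. On their outcome, section 4.5.1 says "We will also compute the proportion of patients who completed germline testing for all eligible prostate cancer patients evaluated in clinic but not enrolled", limited to the study period. No section says where a comparator's test will be looked up, who will look, whether outside tests count, or how long each man is observed. The follow-up section and the schedule of assessments cover session participants only.

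**Bias.** Sections 4.6.1 and 4.6.3 discuss selection and recruitment, not how the outcome is ascertained.

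**The concern.** The primary endpoint is a difference between two proportions, so each must be measured in the same way. Here one cohort has a coordinator through whom decisions and results pass and a stated 24-month capture of deferred decisions. The other has a proportion to be computed by a method the plan does not give. A comparator's test that is not found counts as no test, which lowers only the comparator proportion. If deferred tests in enrolled men are counted for longer than tests in comparators, the difference widens further. Either could yield a significant result in the hypothesised direction when education has no effect, and a larger comparison cohort would not cure it.

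**Working it through.** **The plan's own figure.** Section 4.5.1 says "A sample size of 50 patients produces a two-sided 95% confidence interval on the proportion with a width ranging from 0.27 to 0.29". It ties this to observed values between 0.3 and 0.7 and specifies exact intervals. The Clopper-Pearson interval for n = 50 has width 0.2675 at 15/50 or 35/50, 0.2841 at 20/50 or 30/50, and 0.2895 at 25/50. These round to 0.27 to 0.29, so the figure reproduces. It describes the enrolled proportion alone and says nothing about the comparison.

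**Inputs for the illustration**
- From the plan: 50 enrolled men; Fisher's exact test.
- Assumed, because the plan gives none: 150 comparators; a two-sided 0.05 level; a true testing rate p that is the same in both cohorts (no effect); full capture in enrolled men; a share m of comparator tests missed.

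**Formulas.** The observed comparator rate is p × (1 − m), so the spurious difference is p × m. The chance of a false 'enrolled higher' result is the sum of Bin(x; 50, p) × Bin(y; 150, p(1 − m)) over all pairs (x, y) with Fisher p ≤ 0.05 and x/50 > y/150.

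| True rate p | Missed m | Comparator rate seen | Spurious difference | Chance of false 'enrolled higher' |
|---|---|---|---|---|
| 40% | 0 | 40% | 0 points | 2.1% |
| 40% | 10% | 36% | 4 points | 6.2% |
| 40% | 20% | 32% | 8 points | 15.1% |
| 40% | 30% | 28% | 12 points | 31.4% |
| 20% | 0 | 20% | 0 points | 2.1% |
| 20% | 10% | 18% | 2 points | 4.3% |
| 20% | 20% | 16% | 4 points | 8.5% |
| 20% | 30% | 14% | 6 points | 15.5% |

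**Sensitivity to the assumptions**
- Rate: at p = 30% the figures for 10/20/30% missed are 5.2/11.4/22.4%; at p = 10% they are 3.5/5.7/9.3%.
- A smaller shortfall: 5% missed at p = 40% gives 3.7%.
- Misses in enrolled men too: at p = 40% with 20% of comparator tests missed, the 15.1% falls to 10.0% if 5% of enrolled men's tests are also missed, and to 6.2% if 10% are.
- Comparator number: at p = 50% with 20% missed, the chance is 13.3% with 50 comparators, 16.9% with 100 and 21.7% with 200. More comparators make the false finding more likely.

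**The time window.** Milestones put the start of accrual in October 2021 and database lock in October 2022 or sooner. Even the first man enrolled therefore has about 12 months before lock, against the 24 months in section 3.5. The plan does not say whether deferred tests enter the primary proportion, or up to what date.

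**The case against.** The strongest reply is that the plan is silent on comparator ascertainment, which is not the same as poor ascertainment. These men attend the same single-centre clinics, and section 5.1.2 already has staff reviewing records in Epic, with Slicer Dicer available. Tests ordered within the health system may well be visible, so the main exposure is outside tests, whose frequency nobody has stated. That stands, and it is why this point is a risk and not a demonstrated shortfall. It does not remove the need for a common rule, because the 24-month capture is written for one cohort only.

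Three stronger readings are tempting, but the documents do not support them.

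- *Comparators complete no questionnaire.* Section 5.1.2 describes the Family History Questionnaire as standard in the genitourinary program, so comparators may complete it in routine care.
- *The form removes previously tested enrolled men from the analysis.* Appendix B does ask "Have you ever had genetic testing for cancer risk before", and prior testing is an exclusion. But the form is given at the session, after consent, no section provides for removal on the strength of an answer, and the stated denominator is everyone enrolled. A previously tested man who stays in and is not retested would lower the enrolled proportion.
- *The bias can only favour the intervention.* That needs full capture in enrolled men, which is an assumption; they may defer or ask for genetic counselling, and later tests may be missed. In addition, a man tested in usual care before being approached becomes ineligible to enrol, yet he could be counted as a tested comparator because section 3.2 sets cohort status at the time of analysis. That would raise the comparator proportion.

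The 24-month text is also limited evidence for the primary analysis, given the October 2022 lock. This leaves the window undefined; it does not make it equal.

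**Conclusion.** The concern holds as a risk of unequal capture arising from an unspecified method. Active capture in enrolled men is documented. Less complete capture in comparators is an inference from the absence of any stated contact, source or follow-up. The likely direction favours the intervention, but this is not certain.

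The size cannot be determined from the documents, which give no comparator number, baseline rate or miss rate. Under the assumptions above, missing 10 to 30% of comparator tests lifts the chance of a false positive from about 2% to between 4.3% and 15.5% at a true rate of 20%, and to between 6.2% and 31.4% at 40%. The plan describes current testing as low, so the 20% rows deserve at least as much weight as the 40% rows. The primary comparison should not be run until the rule is written down.

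**What to change.** **In section 4.5.1**, for the Fisher comparison:
- Count a test, in either cohort, only if a germline result or report is in the UCSD record, including scanned outside reports.
- Abstract both cohorts on one form.
- Count only tests within the same fixed number of days from an index date, defined for both cohorts as the first eligible clinic visit in the study period, and before the same data cut-off. State the number of days.
- Judge prior testing by the same chart rule in both cohorts.
- Report separately any later deferred tests and any tests known only from coordinator contact or self-report.
- Add a sensitivity analysis over a range of comparator under-capture. The chart rule makes the method equal but does not recover outside tests that never reached the record.

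**Elsewhere:**
- Reconcile the 24-month follow-up in section 3.5 with the October 2022 database lock in Milestones.
- Document the basis for abstracting comparator charts. The waiver in section 3.2 is for prescreening only, section 5.1.2 says that information will not be re-used, and access for research data is tied to informed consent.

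**Cost.** SAP wording and one shared form, plus possible IRB confirmation of comparator record access, so this is more than an editorial change. Some enrolled men's tests will drop out of the comparison, though they remain in the separate listing.

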Outcome(s): Assess the proportion of patients enrolled in the study who underwent germline testing to the proportion of patients who did not enroll in the study. Assess the effect of a patient educational program on increasing germline genetic testing rate among adult prostate cancer patients who are recommended to receive germline testing per NCCN guidelines. .

Sample Size Estimations: Target accrual is 50 patients in 12 months.

Statistical Analysis: For the primary endpoints of feasibility of implementing an educational intervention, this will be assessed by the accrual rate over 12 months. For the endpoint of efficacy of the intervention in improving rates of germline testing, the proportion of patients who undergo germline testing in this study will be compared to the proportion of patients who undergo germline testing who were eligible, but not enrolled into this study during the study time period.

AMENDMENT HISTORY

Date	Section of study protocol	Amendment or update	Reason
		N/A	

MILESTONES

Milestone	Planned date
Finalize survey instruments	July 2021
Finalize Redcap database along with CRFs	August 2021
Hiring of clinical research coordinator	August 2021
Completion of video	September 2021
Training of research coordinator	August- September 2021
Start of accrual	October 2021
6-month assessment of accrual	April 2022
Database lock	October 2022 (or sooner if 50 patients are accrued)
Analysis	November 2022
ASCO Abstract	January 2023
First Manuscript	March 2023

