2. OBJECTIVES AND HYPOTHESES

2.1 Primary Objective(s) & Hypotheses

Objectives

- (1) To assess the feasibility of a patient educational program to improve germline genetic testing for eligible patients with prostate cancer.
- (2) To assess the effectiveness of a patient educational program with regards to increasing germline genetic testing rate among adult prostate cancer patients who are recommended to receive germline testing per NCCN guidelines.

Hypotheses

- (1) We hypothesize intervention will be feasible with successful recruitment of our target sample size.
- (2) We hypothesize that the rates of germline testing among patients recruited to the study will be higher than rates of testing among patients not enrolled in the study.

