3.2 Study Population

The target population for this study is patients older than 18, with prostate cancer who meet the NCCN criteria for germline testing and who have not undergone prior germline testing.

Subjects will include those patients seen at a facility in the UCSD Health System. Genitourinary oncology clinics will be screened 1 week in advanced for eligible patients. Recruitment procedures will also involve the review of subject records by designated study personnel (e.g., investigators and/or study coordinators) in order to identify potentially eligible subjects. Since Protected Health Information (PHI) will be accessed via the hospital's medical record database and scheduling system (e.g., EPIC/IDX) *prior* to contacting the potential subject about the research study, we have been granted a partial waiver of HIPAA authorization for access to PHI for purposes of prescreening only.

For patients who are eligible for the trial, the investigator will approach the subject and offer participation in the trial. Standard HIPAA authorization to collect research data from the subject's medical record will be obtained at the time of informed consent. Given the COVID-19 pandemic, we are conducting sessions both in clinic and virtually. This will primarily occur via video chat or telephone. Given that this is a low-risk intervention of an educational session, we believe that virtual consenting is also appropriate here given the current pandemic.

For patients who decline the intervention or have not been approached at the time of analysis, these patients will be considered a separate cohort for comparison to the intervention cohort.

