4.1.2 Definition of Comparison Exposure

The comparison group will include individuals with prostate cancer who meet criteria for germline testing however were not approached about participating in the intervention or were approached and declined participating in the educational intervention. In this context, germline testing education will be at the discretion of the treating medical team.

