4.2 Outcomes

Primary Endpoints

1. The proportion of patients who undergo germline testing among those who are enrolled to the study compared to the proportion of patients who undergo germline testing who were eligible, but not enrolled into this study during the study time period
2. Feasibility of implementing an educational intervention for men with prostate cancer at risk of having a hereditary cancer syndrome. This will be assessed by:
 - Accrual rate by month.
 - Proportion of patients who consent to educational intervention among those who are approached (stratified by whether consent was performed in-person or virtually).

Secondary Endpoints

1. Patient understanding of germline testing before and after the education intervention based on questionnaire responses.
2. Patient-reported opinions on germline testing before and after intervention, and patient-reported satisfaction after educational intervention based on questionnaire responses.
3. Physician responses regarding how the germline testing result changed patient management.
4. Prevalence of pathogenic germline mutations among study patients who undergo germline testing.

Exploratory Endpoints

1. Clinical factors (patient and family history, disease characteristics, and outcomes) that are associated with the presence of a germline mutation in a cancer susceptibility gene.

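### The only comparison planned for the effectiveness objective sets consenting men against pooled decliners and un-approached men, with no common time origin or window, so a difference cannot by itself be attributed to education

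*Combined protocol and SAP*

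**What the plan says.** - **Objective and hypothesis (section 2.1).** Objective 2 is "To assess the effectiveness of a patient educational program with regards to increasing germline genetic testing rate". Hypothesis 2 is that "rates of germline testing among patients recruited to the study will be higher than rates of testing among patients not enrolled".
- **Endpoint (section 4.2).** Primary endpoint 1 compares the enrolled proportion with "the proportion of patients who undergo germline testing who were eligible, but not enrolled into this study during the study time period".
- **Comparator (sections 4.1.2 and 3.2).** Comparators are eligible men who "were not approached about participating in the intervention or were approached and declined participating in the educational intervention". Section 3.2 reads membership at the time of analysis and says "these patients will be considered a separate cohort for comparison to the intervention cohort".
- **Entry to the intervention (sections 3.1 and 5.1.2).** The treating physician must approve the approach, and the man must then consent. Section 3.4 excludes men with prior germline testing.
- **Analysis (section 4.5.1).** "The proportion of patients who underwent germline testing in the intervention vs non-intervention cohorts will be compared using" Fisher's exact test. Baseline characteristics are compared, but no adjustment, matching or separate reporting of decliners is planned. The enrolled proportion is computed when the study is complete.
- **Timing.** Section 3.5: "We will capture deferred decisions to pursue germline testing during the 24-month follow up period". The Milestones table starts accrual in October 2021 and puts database lock at "October 2022 (or sooner if 50 patients are accrued").
- **Bias (sections 4.6.1 and 4.6.3).** Recruitment bias is named as a key limitation. The measures offered concern how the study is offered: rotating screening, two languages and a virtual option.

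**The concern.** The objective is causal; the comparison is not built to carry a causal reading. There are two gaps.

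**Selection.** A man already interested in testing is plausibly more likely both to accept a session about it and to be tested. Interest and current intention are asked only of enrolled men, in the Appendix A questionnaire at the start of the session. Nothing in section 4.5.1 separates this from an effect of the session. Pooling decliners with un-approached men also hides the split that would help a reader judge it.

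**Time.** The plan does not say when a comparator starts to be counted, or for how long. For enrolled men, section 3.5 gives 24 months from the session, yet no enrolled man can have 24 months at an October 2022 lock. Two analysts could follow the text and report different primary results. In addition, a man tested in usual care after his first eligible visit but before any approach can count as a tested comparator but can no longer enrol.

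At stake is whether a significant Fisher result would be reported as showing that education raised testing, when selection or timing could have produced it, or whether a real effect could be masked.

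**Working it through.** **1. The plan's own figure.** With n = 50 and the exact (Clopper-Pearson) method, 15/50 gives 0.179 to 0.446 (width 0.267) and 25/50 gives 0.355 to 0.645 (width 0.289). This reproduces the stated 0.27 to 0.29. It describes the enrolled proportion alone and says nothing about the comparison.

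**2. Selection with no education effect.** The documents give no inputs, so all of these are assumed. Let s be the share of interested men, t₁ and t₀ the testing probability in interested and other men, and c₁ and c₀ their consent probability.

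- Overall consent: c = s·c₁ + (1−s)·c₀
- Enrolled: [s·c₁·t₁ + (1−s)·c₀·t₀] / c
- Declined: [s·(1−c₁)·t₁ + (1−s)·(1−c₀)·t₀] / (1−c)
- Un-approached: s·t₁ + (1−s)·t₀
- Number of decliners: 50·(1−c)/c

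Worked case (strong selection: s = 0.6, t = 0.6/0.1, c = 0.7/0.2):

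- c = 0.42 + 0.08 = 0.50, so there are 50 decliners.
- Enrolled: (0.252 + 0.008)/0.50 = 0.52.
- Declined: (0.108 + 0.032)/0.50 = 0.28.
- Un-approached: 0.36 + 0.04 = 0.40.
- Pooled with 100 un-approached men: (50×0.28 + 100×0.40)/150 = 0.36.
- Difference: 0.52 − 0.36 = 16 points.

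Rejection is by exact enumeration of the two-sided Fisher test at 0.05, with 50 enrolled men and 100 un-approached men plus the implied decliners:

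| Assumed case | s; t₁/t₀; c₁/c₀ | Consent | Difference | Rejects |
|---|---|---|---|---|
| No selection (50 vs 150, both 40%) | – | – | 0 | 4% |
| Weak | 0.6; 0.5/0.2; 0.6/0.4 | 52% | 3.7 points | 7% |
| High consent (the weak, middle and strong s and t, with c = 0.9/0.7) | – | 80–82% | 2.5–4.2 points | 5–7% |
| Middle | 0.5; 0.6/0.2; 0.7/0.3 | 50% | 10.7 points | 24% |
| Strong, higher consent | 0.6; 0.6/0.1; 0.9/0.4 | 70% | 12.0 points | 28% |
| Strong | 0.6; 0.6/0.1; 0.7/0.2 | 50% | 16.0 points | 48% |

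Varying the un-approached group from 50 to 300 men gives 2 to 5 points (5–7%) for weak selection or high consent, and 14 to 18 points (43–51%) for the strong case at 50% consent. These are not bounds. If testing tracked consent itself (50% in would-be consenters, 20% in would-be decliners, 150 eligible men, 50% consent), the rates would be 50% and 27.5%, and Fisher would favour the enrolled group with probability 0.75.

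**3. What the split would show.** In the strong case, enrolled minus declined is 0.52 − 0.28 = 24 points, and enrolled minus un-approached is 0.52 − 0.40 = 12 points. In the weak case the two are 6 and 3 points. The pooled figure blends them in proportions set by how many men happen not to be approached.

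**4. Windows, no selection.** Assume a constant testing rate with 20% tested by 12 months.

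- Enrolled at 24 months, comparators at 12: 1 − 0.8² = 0.36, a gap of +16 points.
- Enrolled from session to lock with uniform entry over 12 months, comparators over the full 12: with h = −ln 0.8 = 0.223 per year, 1 − (1 − 0.8)/0.223 = 0.104, a gap of −10 points.
- Same entry pattern and same cutoff in both cohorts: gap 0.

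These show that direction depends on an unstated choice. They do not estimate this study's gap.

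**5. Men tested before any approach.** Section 3.2 limits the target population to men without prior testing, and sections 4.2 and 4.5.1 require comparators to be eligible. Men tested before the study are therefore implied not to be comparators. The open group is men tested in usual care between first eligible visit and any approach. Counting them raises the comparator rate and lowers the difference.

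**The case against.** The best defence is that this is a single-arm pilot and quality improvement initiative, sized for the precision of one proportion. Hypothesis 2 is worded as an association, which Fisher's test addresses. Recruitment bias is openly named as a key limitation, and characteristics will be compared. All of this is true. None of it changes the estimate, and the comparison remains a primary endpoint and the only one offered for an objective about increasing testing.

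It can also be said that selection may matter little. With weak selection or high consent, rejection is 5% to 7% against 4% with none. That stands; the larger figures need strong assumed selection.

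On timing, the 24-versus-12-month contrast cannot arise at the planned lock and would need a later completion date for enrolled men only. The opposite contrast staggers entry for enrolled men alone, although comparators are also seen over the period. A constant rate fits poorly with a decision often taken at the session. These points stand against reading the window figures as likely sizes. They do not remove the ambiguity between sections 3.5, 4.2, 4.5.1 and the Milestones.

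Finally, tests in usual care after a man becomes eligible are largely the outcome that a comparator should show. That is fair, and is why the fix treats those men by sensitivity analysis and does not simply drop them.

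**Conclusion.** The point holds: as planned, a difference in testing between the cohorts cannot by itself be attributed to education, and the plan does not fix the time over which either cohort is counted. It should be corrected before analysis.

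With no education effect and assumed inputs, selection alone gives about 2 to 5 points (5–7% rejection) at the mild end. It gives about 16 points (48%) under strong selection with 50% consent and 100 un-approached men. Unequal windows could move the result either way, and give no gap if entry pattern and cutoff match. Clinician education offered to all oncologists and urologists (section 1.2) could also raise comparator testing. Net size and direction are unknown.

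Three stronger readings are tempting and not supported:

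- That a difference would be no evidence at all. Confounded evidence is weak evidence, and the stated hypothesis is an association that the test does address.
- That men tested before the study inflate the comparator rate. Section 3.2 and the eligibility wording imply that they are excluded.
- That the plan compares 24 months with 12. It leaves the windows unstated, and no enrolled man reaches 24 months by the planned lock.

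**What to change.** Amend section 4.5.1.

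1. **Split the comparator.** Keep the pooled Fisher test as the planned comparison. Add the testing proportion with exact 95% CI for enrolled, declined and un-approached men separately. Give enrolled versus un-approached and enrolled versus declined as descriptive contrasts. Section 4.2 already calls for the proportion consenting among men approached.
2. **Use one time origin and one window.**
   - Take the same origin in every cohort, for example the first eligible clinic visit in the study period while untested, and apply the no-prior-testing criterion at that date.
   - Count tests over the same fixed window, with its length set before analysis. Include only men whose window is complete at data cutoff, or use a time-to-testing estimate with censoring at cutoff.
   - Because enrolled men must stay untested until their session, add a sensitivity result excluding comparators tested before approach or very early after the origin.
   - Report 24-month deferred testing in enrolled men separately.
3. **Limit the claim.** State that the comparison is an association and does not by itself show that education raised testing.

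**Cost.** No added patients, but more than wording. Late entrants are lost or censored, and the conclusion is more modest. The declined group is imprecise if consent is high: at 80% consent, 50/0.80 = 62.5 approached leaves about 12 decliners, and 5 of 12 tested gives an exact 95% CI of 15% to 72%. Record access for non-enrolled men must be confirmed, since section 3.2 limits the waiver to prescreening and section 5.1.2 rules out re-use. The existing plan already raises that question.
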